1.1 Research Background

Chronic obstructive pulmonary disease (COPD) is a progressive chronic lung disease that makes breathing difficult with mucus buildup in the inflamed airway ^(1, 2) and lungs hyperinflation due to expiratory flow limitation. Global Initiative for Chronic Obstructive Lung Disease (GOLD) defines COPD as a common, preventable and treatable disease ⁽³⁾ with significant morbidity and mortality, and incurs intensive expenditure of healthcare resources ⁽⁴⁾. This disease is currently the fourth leading cause of death in the world but is projected to be the 3rd leading cause of death by 2020. In 2012, global death from COPD accounted about 6% which equal to more than 3 million deaths in world population ⁽³⁾. The mortality burden of COPD is expected to rise to 8.6% by 2030 ⁽⁵⁾. In Malaysia, the prevalence of moderate to severe COPD in Malaysia in 2010 is 4.7% which equals to 448,000 cases ⁽⁵⁻⁷⁾.

COPD is attributed by long-term exposure to noxious particles and toxic gases ⁽¹⁾. Tobacco smoking is the main cause of COPD globally ⁽⁸⁾. The Third National Health and Morbidity Survey (NHMS III) conducted in Malaysia in 2006 showed that the prevalence of male ever smokers was 57.6% and in female is 2.5% ⁽⁹⁾. Other than that, inhalation of organic or chemical dust and fumes, and biomass exposure also among the risk factors of COPD. Exposure to noxious particles will cause activation of inflammatory immune responses. However, continuous and repetitive exposure towards these noxious particles will lead to tissue remodelling in small airways causing smooth muscle hypertrophy and fibrosis causing major site of obstruction in COPD ⁽¹⁰⁾.

COPD is characterized by a mixture of small airway disease and parenchymal lung tissue destruction causing emphysema which affecting gas transfer ⁽¹¹⁾. Small airway is defined as airways of less than 2mm in internal diameter which lacks in cartilage, and have greater proportion of smooth muscles with fewer goblet cells in the epithelial layers ⁽¹¹⁾. Approximately 10-25% of total airways resistance in healthy lungs is due to the small airways, with their contribution to total airways resistance increasing substantially in COPD. As the small airways are located in the lung periphery, they are not easily evaluable, which can potentially interfere

with the diagnosis (especially at early stages), monitoring, detection of responses to clinical interventions, and prognostic evaluation in COPD ⁽¹²⁾.

In COPD patients, the small airways represent the key sites of airflow obstruction, and small airway disease (SAD) is considered a functional hallmark of disease ⁽¹³⁾. The presence of SAD progressively increases with higher GOLD classifications and it is closely related to the high impact of disease measured by COPD Assessment Test (CAT) questionnaire. Distributions of SAD among COPD patients classified according to GOLD classification. In each of GOLD A, B, C and D class, the prevalence of SAD are 49%, 88%, 61%, and 96% respectively (**Figure 1**) ⁽¹³⁾. As presence of SAD is closely related to high impact of disease with CAT score ≥ 10 , they tend to have more symptoms ⁽¹³⁾.

[figure not shown]

Figure 1: Distribution of patients with and without SAD according to the GOLD classification ⁽¹³⁾

1.2 Problem Statement

As mentioned before, in COPD patients, the small airways represent the key sites of airflow obstruction, and SAD is considered a functional hallmark of disease ⁽¹³⁾. Spirometry is the most reproducible and objective measurement of airflow limitation ⁽³⁾. However, it is not sensitive to evaluate SAD. In the context of lung function evaluation, the impulse oscillometry system (IOS), a type of forced oscillation technique, was recently proposed as a better way of detecting SAD than standard spirometry. IOS provides measurement for both proximal and distal airway resistance. In COPD patients, IOS is also useful to detect early phases of disease,

other than useful to assess bronchodilator responsiveness and effect, as well as to define different subgroups of patients according to airflow obstruction. SAD measured by IOS increases progressively according to the severity of disease assessed by GOLD classifications in COPD ⁽¹³⁾.

The earliest indication of small airways disease when evaluated by spirometry is the deceleration of airflow at the terminal portion of the flow-volume curve, which can be detected by measuring the mean expiratory flow between 25% and 75% of Forced Vital Capacity (FVC) (FEF_{25-75%}). This parameter is calculated by dividing the expiratory volume by the time difference between these two points in the mid-range of the FVC manoeuvre ⁽¹²⁾. The use of FEF_{25-75%}/FVC can act as a potential clinical tool for early detection of COPD ⁽¹²⁾. Thus, patients who present with low FEF_{25-75%} values should be monitored closely, as they are susceptible to COPD, even though they may have normal lung function ⁽¹⁴⁾.

IOS is a simple, non-invasive method requiring only passive patient cooperation without special manoeuvre for evaluation of lung function through the measurement of both airway resistance and airway reactance.⁽¹⁵⁾ The pressure-flow oscillations are applied at the mouth superimposed on the subject's tidal breaths to measure respiratory system resistance and reactance at different oscillation frequencies. It uses sound waves to rapidly detect airway changes. When analysed, these pressure signals separately quantify the degree of obstruction in the central and peripheral airways ⁽¹⁵⁾. In IOS, it enables measurement of total respiratory resistance (R5) and proximal respiratory resistance (R20), with the R5-R20 difference reflecting small airway resistance ^(16,17). Small airway disease is significant if $R5-R20 > 0.71$ cmH₂O/L/sec ⁽¹⁷⁻²⁰⁾.

Treatment of COPD requires combination of pharmacological and non-pharmacological approaches. In non-pharmacological treatment, chest physiotherapy and pulmonary rehabilitation is the cornerstone of management of COPD patients. It can result in improvement of symptoms, increased exercise capacity, and improvement in lung functions ⁽²¹⁾. By early detection of SAD in COPD, it enables the physician to offer patients with a more targeted approach therapy, for example the use of small particle size inhalers or mechanical intervention for example oscillating positive expiratory device (OPEP), such as Aerobika®.

1.3 Research Question

Can Aerobika® OPEP device improve small airway disease and CAT score in COPD on top of standard therapy.

1.4 Hypothesis

Aerobika® OPEP improves small airway parameters and CAT score on top of standard therapy.

CHAPTER 2

LITERATURE REVIEW

In healthy people, mucociliary clearance and cough mechanisms are normally effective and efficient, but become overloaded if these systems malfunction and in the presence of excessive bronchial secretions. Chest physiotherapy is commonly used to improve the mobilization and removal of airway secretions in patients with respiratory dysfunction ⁽²²⁾. Other non-pharmacological therapy such as active cycle of breathing technique (ACBT) , positive expiratory pressure (PEP), oscillating PEP (OPEP) devices, and intrapulmonary percussive ventilation (IPV) are also known helpful in airway clearance ⁽²³⁾. Techniques may be used alone or in combination with others.

OPEP device has been developed since 1970s , and it was first developed and described in Switzerland, as an adjunct or supplement to traditional airway clearance methods ^(22, 23). It has been utilized to promote the clearance of respiratory secretions in individuals with impaired ability to cough, particularly in chronic diseases. It is a hand-held, drug-free medical device that is designed to expand the airways, mobilize mucus, and help to expel mucus from the lungs. It has been shown to improve health-related quality of life and improve lung function in COPD patients ⁽²⁴⁾.

During inhalation of OPEP, it will provide a linear pathway through an inhalation valve. Upon exhalation, a one-way valve within the device mechanism opens and closes intermittently resulting in positive pressure that will hold airways open and sustaining expiratory flow, combines with airway vibrations or oscillations resonating at a frequency similar to the cilia which decrease the viscoelastic properties of the mucus ^(23, 25-27). This will thin and help to mobilise sputum, making it easier for removal by deep force exhalations or coughing (“huffing”) techniques (**Figure 2**) ⁽²³⁾. There are few models of OPEP devices, for example Aerobika® (Trudell Medical International), Acapella® (Smiths Medical), Flutter® (Axcan Scandipharm), Lung Flute® (Medical Acoustics), and Quake® (Thayer Medical).

The Aerobika® OPEP device has been reported to improve symptoms and quality of life outcomes for COPD patients with mucus hypersecretion. This compares the responder rates from two separate studies using the same device, one with the St George’s Respiratory Questionnaire (SGRQ) and the other with the CAT score. First study done by Svenningsen et.

al. in 2016 is a randomized cross-over study in 27 COPD patients for 3-4 weeks, used the SGRQ. In their study, the mean SGRQ value for the 14 COPD patients with chronic bronchitis significantly improved from 49 to 40 ($p = 0.01$, paired t-test) following OPEP therapy. SGRQ is a standardized self-administered airways disease-specific questionnaire that divided into three subscales: symptoms, activity, and impacts. Overall, SGRQ is interpreted as quality of life scores⁽²⁵⁾. Second study by Sugett J. is a clinical assessment of 37 COPD patients over an 8-week period, used the CAT score. In this study, the mean CAT value for the 26 COPD patients with chronic bronchitis significantly improved from 19.7 to 17.4 ($p = 0.01$, paired t-test) following OPEP therapy. Even though using different validated questionnaire instruments, the results from these two separate studies show good agreement, with nearly two thirds of COPD patients with chronic bronchitis exhibiting clinically significant improvements. In terms of responder rate analysis, Aerobika® OPEP showed significant improvement in symptoms and quality of life greater than the Minimum Clinically Important Difference (MCID), where it proved 64% improvement in SGRQ (MCID ≥ 4) and 62% improvement in CAT score (MCID ≥ 2).⁽²⁸⁾ MCID is the smallest change in score that patients perceive as beneficial or detrimental, and is useful to aid the clinical interpretation of health status data, particularly in response to intervention. The most reliable estimate of the MCID for SGRQ is 4 points⁽²⁹⁾, whereas of the CAT score is 2 points.⁽³⁰⁾

It is postulated that OPEP will help to increase exercise capacity in COPD patients. In a study done by Nicolini and colleagues in 2018, patients involved in the study were given Lung Flute® OPEP. In their study, OPEP users demonstrated improvement in exercise capacity measured by using 6 minutes walking test (6MWT) compared to control group ($p < 0.008$ vs 0.01). They also showed improvement in COPD symptoms compared to control group assessed by using CAT score ($p < 0.004$ vs $p < 0.012$), and the Modified Medical Research Council (MMRC) Dyspnoea Scale ($p < 0.002$ vs $p < 0.012$). However, in their study, OPEP has not shown a reduction number of exacerbation in the involved patient.^(31, 32)

Improvement in exercise capacity is also proved by a study done by Svenningsen et. al in 2016 in sputum-producer patients. Patients fitted into sputum-producers criteria if they had coughed and brought up sputum “several days a week” (>2 days a week) or “almost every day” in the month prior to the study. Exercise capacity is assessed at baseline, and after Aerobika® OPEP usage at week 3 to 4, and also during final visit at week 6 to 8 using 6MWT. All participants were trained by a pulmonary function technologist to use the device four-times

daily with each session consisting of 10–20 blows into the device, followed by 2–3 “huff” coughs. Treatment sessions were documented at home by the patient using a daily diary. Post OPEP study, in sputum-producers only, it showed significant improvement in 6MWT with p -value of 0.04 compared to pre-OPEP group. Their study also proved that the spirometry result (FVC value) in sputum-producer patients with OPEP showed significant improvement compared to off-OPEP group (6% improvement in FVC, $p = 0.02$).^(25, 32)

Additionally, Aerobika® OPEP will help to reduce moderate to severe exacerbation. The risk of experiencing subsequent exacerbations is two to four times higher in COPD patients with a prior exacerbation compared to those without prior exacerbation. Therefore, prevention is an important treatment goal⁽³³⁾. In a study done by Burudpakdee and colleagues in 2017, significantly fewer patients provided with the Aerobika® OPEP device compared to matched controls experienced moderate-to-severe exacerbations (18.5% vs 25.7% respectively, $p = 0.014$) or severe exacerbations (13.8% vs 19.0%, respectively, $p = 0.046$) in 30 days.⁽³⁴⁾

There is a study showed that Aerobika® is the most effective OPEP in reducing COPD re-exacerbations compared to other OPEP devices. In a study done by Tse et. al. in 2020 on comparison of impact between two-commonly used OPEP devices; Aerobika® and Acapella® in COPD or chronic bronchitis patients, patients using Aerobika® OPEP had a 31% reduction in COPD or chronic bronchitis related readmission within 30 days of the index hospitalization (12.0% vs. 17.4%; $p = 0.001$) compared to Acapella. This significant difference persisted over a 12-month duration, with a smaller proportion of Aerobika® patients having a severe exacerbation requiring hospitalization (39.6% vs. 45.3%; $p = 0.013$) and fewer hospitalizations per patient (mean, 0.75 vs. 0.90; $p = 0.010$). Aerobika® users also have significantly longer time to first severe exacerbation than Acapella users (log-rank $p = 0.01$). This suggests that Aerobika® OPEP device may be a beneficial add-on to usual care and that OPEP devices may vary in clinical effectiveness.⁽²⁶⁾

There is evidence for the cost-effectiveness of the Aerobika® device in the management of COPD, in terms of savings in direct medical costs associated with reduction in COPD exacerbations. By using real-world clinical evidence to evaluate the incremental performance of the Aerobika®, Khoudigian-Sinani et. al. in 2017 analysed data from published literature and national fee schedule to model the cost-effectiveness of Aerobika® OPEP in patients who had experienced an exacerbation in the previous months, or post-exacerbation care population. When the effect of Aerobika® device was assumed to last 30 days, use of the

device resulted in improved outcomes (six fewer exacerbations per 100 patients per year) lead to cost-savings, compared to no OPEP therapy ⁽²⁾. Similar analysis was done by Thanh and colleagues in 2019 which showed that the Aerobika® OPEP is a potential component of a treatment strategy for symptom control and reduce the risk of re-exacerbations in patients with COPD, with more effective and less costly economic outcome ⁽²⁴⁾. Therefore, Aerobika® device is a treatment option that provides clinical benefit and results in direct medical cost savings in a post-exacerbation care COPD population in a long run. In real population, usage of OPEP device may be beneficial as it can reduce visits to the emergency department, reduced early rehospitalizations and lower the treatment cost by the means of reducing COPD exacerbation ^(26, 34, 35).

On the other hand, there is only one study measures the outcome of sputum clearance in COPD patients with OPEP. Svenningsen and colleagues in a study done in 2016 proved that OPEP statistically and clinically significant helpful in improving sputum clearance in sputum-producers COPD patient. Patient Evaluation Questionnaire (PEQ)-ease-bringing-up-sputum score (pre-OPEP 3.9 ± 0.8 , post-OPEP 2.7 ± 1.1 ; $p = 0.005$) is used for evaluation, at which this context, a reduced PEQ score indicates improved sputum clearance ^(25, 32).

In COPD, sputum clearance might be expected to reduce airflow limitation and allow occluded lung units to be recruited. It is postulated that usage of OPEP can improve small airway disease parameters using IOS. At the moment, there are no studies available on small airway disease parameters improvement after OPEP usage.

In summary, this study would like to propose that non-pharmacological treatment for airway clearance is as important as pharmacological therapy. The aim of the study is to demonstrate that the usage of Aerobika® OPEP device among COPD patients may augment sputum clearance, improve small airway parameters by IOS as well as patient's symptoms as measured by CAT score. In addition, it will also help to improve exercise quality as well as lung function in this group of people.

[figure not shown]

Figure 2: Oscillating positive expiratory pressure (OPEP) mode of action model ⁽²³⁾.

Figure 3: Aerobika® OPEP device

CHAPTER 3

RESEARCH OBJECTIVES

3.1 Objectives

3.1.1 Primary

To demonstrate improvement of small airway parameter using IOS after introduction of Aerobika® OPEP in 3 and 6 months among COPD patients in UKMMC.

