4.5 Sample Size

[figure not shown]
According to Cohen's d formula, Cohen suggested that effect size of 0.2, 0.5 and 0.8 as small, medium and large effect size respectively. Effect sizes are the most important outcome at which the researchers want to know whether an intervention or experimental manipulation has an effect greater than zero, or (when it is obvious an effect exists) how big the effect is⁽⁴⁰⁾. In our study, we aim to have a medium effect size with the usage of Aerobika®. An effect size of 0.5 is described as medium and is 'large enough to be visible to the naked eye'⁽⁴¹⁾.

By using online statistical calculator apps; Sample Size Calculator for Comparing Paired Differences, this study would require a sample size of 34 to achieve a power of 80% and a level of significance of 5% for detecting an effect size of 0.5 paired differences (Dhand, N. K., & Khatkar, M. S. (2014). Statulator: An online statistical calculator. Sample Size Calculator for Comparing Two Paired Means. <http://statulator.com/SampleSize/ss2PM.html>.

Additional of 40% samples is recruited to avoid subject consent withdrawal, drop out, or missing data. Therefore, a total of minimum 48 patients will be recruited for this study. However, we aim to recruit 60 patients as we were sponsored 60 units of Aerobika® OPEP.

The outcomes of this study will be evaluated on all patients by comparing all the parameters during baseline and at 3- and 6-months follow-up after using Aerobika®. There will be no non-interventional arm as the sample size will become bigger. During the COVID-19 pandemic era, we would like to reduce the exposure towards those performing respiratory tests. The other limitations as well with larger sample size are budget and time constraint.

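### The primary objective fixes neither the IOS measure nor the primary visit, so a fall in R5 (total resistance), or a result at either visit, could be reported as the primary small-airway success

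*Combined protocol and SAP*

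**What the plan says.** Section 3.1.1 sets the primary objective as "To demonstrate improvement of small airway parameter using IOS after introduction of Aerobika® OPEP in 3 and 6 months". The measure is in the singular and unnamed, and the two time points are not ranked. The hypothesis in 1.4 uses the plural: "Aerobika® OPEP improves small airway parameters and CAT score on top of standard therapy". The summary closing Chapter 2 also uses the plural: "improve small airway parameters by IOS as well as patient's symptoms as measured by CAT score". Section 4.3 schedules IOS at weeks 12 and 24 without naming a measure, and the data collection sheet (Chapter 9) has rows for R20, R5 and R5-R20 at weeks 0, 12 and 24.

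Section 1.2 says what the measures mean: "it enables measurement of total respiratory resistance (R5) and proximal respiratory resistance (R20), with the R5-R20 difference reflecting small airway resistance". Inclusion criterion VII uses R5-R20 > 0.71 cmH2O/L/sec to define small airway disease at entry. Neither place declares R5-R20 to be the endpoint.

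Section 4.5 asks for 34 patients for a paired effect size of 0.5, 80% power and 5% significance, without tying that effect to a measure or visit. It then describes the evaluation as "comparing all the parameters during baseline and at 3- and 6-months follow-up".

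**The concern.** Chapter 2 states that no study has yet looked at small-airway parameters after OPEP use, so a small-airway effect is the trial's new claim. There is no control arm (4.5), and a clearly fixed primary outcome is one of the few safeguards left.

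Two choices remain open. The first is the measure. R5 contains the small-airway component but also the proximal one, so it can fall with no change in the small airways. That is a plausible route here: patients are enrolled for mucus hyperproduction, and the device is meant to clear airway secretions. The second is the visit: a result at 3 months, at 6 months or at both could be called success. Each open choice raises the chance of a false improvement above that of the one comparison that was sized, and the first also allows a large-airway change to carry a small-airway label.

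**Working it through.** **1. The plan's own figure.** Inputs from 4.5: d = 0.5, power 80%, significance 5% (sidedness not stated). For a two-sided paired test, n ≈ ((1.96 + 0.842)/0.5)² + 1.96²/2 = 31.4 + 1.9 = 33.3, so 34. The exact noncentral-t calculation also gives 34 (power 80.8% at 34, 79.5% at 33). Adding 40% gives 34 × 1.4 = 47.6, so 48. The stated figures reproduce, for one paired test.

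**2. False improvement when R5 or R5-R20 may count.** Write D = R5-R20, so R5 = R20 + D. Let s = SD of change in R20 divided by SD of change in D, and r = correlation of those two changes. Then corr(R5, D) = (1 + rs)/√(1 + s² + 2rs). The documents give none of these quantities. Assumed ranges: s 0.5-0.8, r 0-0.4, correlation between visits 0.5-0.8. Each test is two-sided at 5%, so one named test has a 2.5% chance of false improvement. Simulation of correlated normal test statistics with no true effect (400,000 draws):

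| s | r | corr(R5, D) | one visit | two visits (between-visit correlation 0.8 to 0.5) |
|---|---|---|---|---|
| 0.5 | 0 | 0.89 | 3.5-3.6% | 5.4-6.3% |
| 0.5 | 0.4 | 0.93 | 3.3-3.4% | 5.2-6.0% |
| 0.8 | 0 | 0.78 | 3.9-4.0% | 6.0-7.2% |
| 0.8 | 0.4 | 0.87 | 3.6-3.7% | 5.6-6.5% |

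This is about 3.3-4.0% at one visit and about 5-7% over two, against 2.5%.

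**3. The visit alone.** With R5-R20 fixed but either visit allowed to count, the chance of at least one two-sided p < 0.05 is about 8-9%, against 5%. The independence bound is 1 - 0.95² = 9.8%.

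**4. Illustration of mislabelling.** Suppose R20 truly improves by d = 0.5, D does not change, and the two changes are uncorrelated. The standardised effect on R5 is 0.5s/√(1 + s²). Power for a two-sided 5% paired test:

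| s | effect on R5 | n = 34 | n = 60 |
|---|---|---|---|
| 0.5 | 0.224 | 24% | 40% |
| 0.8 | 0.312 | 42% | 66% |
| 1.0 | 0.354 | 52% | 77% |

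R5-R20 itself would show a false improvement about 2.5% of the time. Over wider assumptions (s up to 2, r up to 0.6) the R5 figure at n = 34 runs from 18% to 72%.

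**The case against.** The best defence is that R5-R20 is already the natural reading. The objective is limited twice, to a small-airway parameter and to IOS. Section 1.2 assigns R5 to total and R20 to proximal resistance, and inclusion VII defines the disease by R5-R20 alone. This narrows the gap but does not close it. R5 remains an easy substitute because it includes the small-airway component, the hypothesis and the Chapter 2 aim speak of parameters, and nothing ranks the visits.

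A reader might infer more: that any of the three IOS rows, or FEF25-75, could count as primary success. The documents do not support that. Calling a fall in R20 small-airway improvement would contradict 1.2. FEF25-75 is introduced there as a sign seen "The earliest indication of small airways disease when evaluated by spirometry", so the words limiting the objective to IOS exclude it; it belongs with the spirometry objective in 3.1.2. Error figures that rely on those two routes are therefore left out. Likewise, the sentence in 4.5 about comparing all parameters describes the evaluation in general and sets no rule for primary success.

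It is also fair to object that the proximal-effect figures depend on an assumed R20 effect, no small-airway change at all, and assumed SD ratios. They are conditional, and should not be read as an expected error rate. Restricting s to 0.5-0.8, as in step 2, lowers the upper end at n = 34 from 52% to 42%.

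**Conclusion.** The point holds as a gap in the specification of the primary endpoint: measure and visit are both open, while the sample size serves one paired test. The statistical inflation is modest: about 3.3-4.0% false improvement at one visit and 5-7% over two, against 2.5%; for R5-R20 alone over two visits, about 8-9% two-sided against 5%. The more serious consequence is interpretive, because a large-airway effect could reach significance on R5 and be reported as the small-airway result. The 24-52% at n = 34 shows that this could happen readily under the stated conditions, not how often it will. All these percentages rest on assumed correlations and, except for the visit-only figure, on assumed SD ratios. That measure and visit are unnamed rests on the text alone.

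**What to change.** Rewrite 3.1.1 to name change from baseline in R5-R20 (cmH2O/L/sec) at one stated visit, 3 or 6 months at the sponsor's choice, as the single primary outcome. Report the other visit as supportive, and show R5 and R20 beside R5-R20 as its components, also supportive. Keep FEF25-75 under the spirometry secondary objective in 3.1.2. Reword 1.4 to match, and state in 4.5 that the effect size of 0.5 refers to this outcome.

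The cost is wording only: everything is already collected, and n = 34 applies unchanged. The small downside is that a result on R5 alone, or at the other visit alone, can no longer be called primary success. Keeping both visits as primary with a Bonferroni correction would instead need 41 evaluable patients for 80% power at d = 0.5; with 34, power would be 71%.
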